*****REDACTED FOR PUBLICLY POSTED PROTOCOL*****

2 STUDY OVERVIEW AND PROTOCOL SUMMARY

Study population: Patients (inpatient and outpatient) of all ages two months and older who present with fever to selected health facilities in sub-Saharan Africa and Southeast Asia, and community controls.

Number of Sites: Five; in 1) Lao PDR, 2) Malawi, 3) Mozambique, 4) Myanmar, and 5) Zimbabwe.

Study duration: 12 months of participant recruitment at each site; to be extended at individual sites if required to meet sample size target.

General objectives: To identify the causes of fever, and the antimicrobial susceptibility of bacterial pathogens causing fever, in low- and middle-income settings where few data are available.

Specific primary objectives:

- 1) To determine the treatable and/or preventable causes of fever in children and adults presenting as outpatients, and among those admitted to hospitals, in areas represented by the study sites;
- 2) To determine how fever aetiology varies according to patient age, geographical area, local malaria and HIV prevalence, and other risk factors;
- 3) To determine the prevalence and spectrum of antimicrobial resistance among bacteria identified in clinical specimens from febrile patients.

Specific secondary objectives:

- 1) To generate data on incidence of specific infections in study site catchment areas, and therefore contribute key data on disease burden for some infections that are not counted in current “global burden of disease” estimates;
- 2) To build an archive of well-characterised and geographically diverse biological samples from well-characterised clinical phenotypes for use in evaluation of new diagnostic and prognostic tests, and in identification of human- and pathogen-related biomarkers that may improve case management strategies;
- 3) To evaluate available biomarker assays to assess their performance and potential utility in fever case management in the study areas;
- 4) To generate data to inform the development of new fever case management algorithms which may be evaluated in future studies.

3 BACKGROUND AND RATIONALE

3.1 Background Information

3.1.1 Current status of fever case diagnosis and management in malaria-endemic areas

Fever is one of the most common symptoms leading to health care seeking and hospital admission in sub-Saharan Africa and Asia.^{1,2} Current WHO algorithms for the primary care level do not provide comprehensive guidance to clinicians for the management of non-malarial fevers. If the malaria test is negative, the patient is classified as “Fever: no malaria” in the Integrated Management of Childhood Illness (IMCI) guidelines³ or in the Integrated Management of Adolescent and Adult Illness (IMAAI) guidelines⁴ and advice is given to “treat according to the apparent cause of fever.” Many febrile illnesses present with non-specific symptoms and signs, and the current recommendations often result in treatable diseases being left untreated or treated with inappropriate antimicrobials, on the one hand, and over-treatment of self-limiting conditions with antimicrobials on the other, with important implications for the development of antimicrobial resistance.^{5,6}

3.1.2 Current knowledge of causes of fever in malaria-endemic areas

Little is known about the non-malarial causes of fever in many parts of the world,⁷ so there is sparse evidence on which to base empirical treatment guidelines for febrile patients testing negative for malaria. A few studies provide some indication of the clinical spectrum of febrile illness,^{8,9} but these studies were often disease specific, for example focussing on urinary tract infections in Nigeria¹⁰ or arboviruses in Asia.¹¹

Members of our group have recently reviewed⁷ and mapped¹² the currently available data on causes of fever in patients attending health facilities in sub-Saharan Africa and Southeast Asia. In addition, a few studies specifically designed to look at aetiologies of fever have been recently published.^{2,13-16} While the results are useful within the specific study areas, the study designs were heterogeneous – with differences in patient age, type of health facility, seasons covered, inclusion criteria, and study design – making it difficult to compare findings across sites and produce a clear picture of the causes of fever in each age group and at each level of care. In addition, there is heterogeneity in laboratory case definitions used; use of diagnostic tests that are not sufficiently validated or not widely accepted; and lack of control groups, preventing calculation of attributable fractions.

In particular, there is very little information on incidence for many of the infections thought to be clinically important at the FIEBRE study sites, and consequently little information on which to base estimates of burden of disease, or to guide empirical therapy or control measures.¹⁷

3.1.3 Fever case management and antimicrobial resistance

The ability to differentiate between bacterial and viral infections could have a major global impact on antimicrobial resistance by limiting the unnecessary use of antimicrobials. The WHO convened a meeting of experts in September 2015, including members of our group, on biomarkers to discriminate bacterial from other infectious causes of fever.¹⁸ The conclusion of the meeting was that the evaluation of biomarker tests to distinguish between bacterial causes of fever requiring antimicrobial treatment, and self-limiting viral infections, in low-income settings was a very high priority.

3.2 Significance and Scientific Rationale

This study, titled Febrile Illness Evaluation in a Broad Range of Endemicities (FIEBRE), is proposed to help to fill key information gaps by means of a multi-site investigation, using consensus clinical, laboratory, and social science protocols, in regions with a high burden of infectious disease from which few or no data are available.

We will conduct a study on causes of febrile illness, and antibacterial resistance, at five sites in sub-Saharan Africa and Southeast Asia. We will focus on detecting infections that are treatable (e.g. with specific antimicrobials) and/or preventable (e.g. with vaccination or vector-control approaches). We will use a common design, with harmonised inclusion criteria, case definitions, laboratory procedures, and result interpretation. This approach will generate reliable and comparable data that can contribute to updated recommendations on the clinical management and prevention of febrile illnesses, adapted to local contexts. The results of this study will provide data to support more reliable estimates of the incidence and, in turn, burden of disease, and updated evidence-based algorithms for the management of febrile illness; and will provide a basis for future evaluation of novel diagnostics, and rational approaches to disease surveillance.

We will study adults and children, and both outpatients and inpatients from the same facilities or catchment areas. Because the vast majority of patients attending health facilities with fever are not admitted to hospital, data on outpatients are essential to guide the development of clinical management guidelines including strategies to improve targeting of antimicrobials. The goal of the study in outpatients is to identify treatable and preventable causes of fever, with a view to optimising appropriate antimicrobial prescribing to reduce the spread of antimicrobial resistance, while ensuring the best possible clinical outcomes. It is also critical to understand the causes of severe illness and death to design empiric treatment regimens that are effective, so the inclusion of inpatients is essential. The goal of the inpatient study is similar, with a view to reducing the case fatality ratio by improving the matching of antimicrobials with the aetiology of severe disease.¹⁹

Control participants will be enrolled from the communities surrounding participating health care facilities for two reasons. First, interpreting the results of some diagnostic tests requires knowledge of background prevalence of infection or colonization in the study population. Community controls will provide samples to estimate this background for each study site. Second, a healthcare utilisation survey (focusing on fever episodes and treatment seeking) administered to control participants will allow us to estimate the incidence and burden of specific causes of fever in the study settings.

This study provides a unique opportunity to collect and store biomedical samples with data from a large and well-characterised group of febrile patients and controls from representative settings in sub-Saharan Africa and Southeast Asia. The samples will be useful for identification of novel diagnostic targets, and for development and evaluation of new point-of-care diagnostic tests intended to guide the management of febrile patients. New tests could include those that predict severity of illness, detect specific infections, and/or differentiate between bacterial and viral infections, as identified as a high priority at a WHO meeting of experts convened in 2015.¹⁸ Informed consent will be sought for study participation, and for storage and future use of data and biological samples.

For clinicians to be able to appropriately use new knowledge on aetiologies of fever, diagnostic tests, and antimicrobial resistance data to manage febrile patients, research evidence must be integrated into clear guidelines. Implementation of clinical algorithms,

such as IMCI or integrated Community Case Management (iCCM), has shown that health care workers are able to adopt and apply recommendations when reasonable support is provided.²⁰ The design and support for these guidelines must take into account end users' perceptions and patients' preferences in order to ensure good adherence and optimise impact. These issues will be addressed in qualitative work conducted alongside and linked to the FIEBRE study, which will be presented in a separate social science research protocol.

4 STUDY OBJECTIVES

4.1 General objective

To identify the causes of fever, and the antimicrobial susceptibility of bacterial pathogens causing fever, in low- and middle-income country settings where few data are available.

4.2 Specific primary objectives

- 1) To determine the treatable and/or preventable causes of fever in children and adults presenting as outpatients, and among those admitted to hospitals, in areas represented by the study sites;
- 2) To determine how fever aetiology varies according to patient age, geographical area, local malaria and HIV prevalence, and other risk factors;
- 3) To determine the prevalence and spectrum of antimicrobial resistance among bacterial pathogens identified in clinical specimens from febrile patients.

4.3 Specific secondary objectives:

- 1) To generate data on incidence of specific infections in study site catchment areas, and therefore contribute key data on disease burden for some infections that are not counted in current "global burden of disease" estimates;
- 2) To build an archive of well-characterised and geographically diverse biological samples from well-characterised clinical phenotypes for use in evaluation of new diagnostic and prognostic tests, and in identification of human- and pathogen-related biomarkers that may improve case management strategies;
- 3) To evaluate available biomarker assays to assess their performance and potential utility in fever case management in the study areas;
- 4) To generate data to inform the development of new fever case management algorithms which may be evaluated in future studies.

5 SUMMARY OF STUDY DESIGN

FIEBRE is a study of febrile illness in people aged two months and older residing at one of five sites (three sites in sub-Saharan Africa, two Southeast Asia). Patients who present with fever at the selected facilities will be recruited (Day 0) if they or their guardians/caregivers (in the case of minors) provide written informed consent. Study staff will take a targeted illness and exposure history, and perform a physical examination. Pharyngeal swabs and a venous blood sample will be collected from all participants; a urine sample will be collected from selected participants. Tests for malaria and for HIV (at sites where HIV prevalence exceeds 1% in the general adult population, for patients not already known to be infected), serum cryptococcal antigen (CrAg) and urine lipoarabinomannan (uLAM, a marker of active tuberculosis infection) point-of-care tests (for subsets of patients), and blood cultures will be performed on site; bacteria and fungi isolated from clinical specimens will be identified and tested for antimicrobial susceptibility.

Study patients will be managed by the clinical staff responsible for usual patient care at each study site, according to local standard of care. Results of malaria tests, HIV tests, CrAg and uLAM tests, blood and urine cultures, and antimicrobial susceptibility testing will be provided to the clinical staff as soon as available. Serology and other laboratory tests will be performed at internationally recognised reference laboratories. At Day 28 after enrolment, study patients will be asked to provide a further blood sample for serology and clinical outcome will be evaluated.

Recruitment to the study will be over a 12-month period to ensure that seasonal variations in causes of fever are captured. Background prevalence of specific infections in the study population at each site will be estimated with blood and pharyngeal samples from community controls. In addition, control participants will be surveyed to obtain representative data about treatment seeking and medicines use. By combining data on causes of fever at study sites with the estimate of the proportion of patients with fever seeking care at those facilities, we will estimate the incidence of common infections in the study areas, in order to contribute to efforts to define burden of disease.²¹⁻²⁴ A separate protocol will be prepared and submitted for ethics approval describing in-depth qualitative

research on fever management and local concepts related to antimicrobials, to be conducted in the same study areas.

6 STUDY POPULATION AND SELECTION CRITERIA

Participants will be patients who present with fever for health care at the selected health care facilities. Patients of all ages two months and older will be eligible for enrolment. Study sites include outpatient and inpatient facilities in Laos, Malawi, Mozambique, Myanmar, and Zimbabwe. Patients will be recruited if they fulfil all of the following criteria (see also section 7.2 on participant enrolment, and Screening and Enrolment Forms [Appendix C]):

- 1) Tympanic or axillary temperature $\geq 37.5^{\circ}\text{C}$ at presentation;
- 2) Not having been hospitalized or having undergone surgery in the previous month;
- 3) Age ≥ 2 months (two months or older);
- 4) For outpatients, residence (at the time of enrolment) within the defined catchment area around the health facility (see section 7.5.1);
- 5) For outpatients aged ≥ 15 years, absence of symptoms of lower respiratory infection and of diarrhoeal diseases as defined by:
 - a) cough AND ≥ 1 of the following: cough productive of green/yellow sputum, or haemoptysis;
 - b) ≥ 3 loose stools within the previous 24 hours;
- 6) For outpatients aged ≥ 2 months to < 15 years, absence of symptoms of diarrhoeal diseases as defined by: ≥ 3 loose stools within the previous 24 hours;
- 7) Willingness and ability to provide demographic and clinical information, and clinical samples, at the time of enrolment and 28 days later;
- 8) Provision of written informed consent for adult participants; or for children, provision of written consent from a parent/guardian and assent from the child (according to local regulations and practices at each study site).

Controls will be community members in the study site health facilities' catchment areas, frequency matched to participants by age and season (see section 7.5 for details of selection and study activities for community controls).

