7.5.1 Selection and recruitment of community controls

To define the catchment area for outpatients and community controls, existing data and pilot data from each site will be combined to define an area around the study facility in which approximately 80% of outpatients live. Residing within this area will be a selection criterion for FIEBRE outpatients (section 6). Community controls will be recruited within this area, individually matched to participating outpatients.

During each month of the study at each site, half of the outpatients will be selected at random (or by taking every second outpatient in chronological order of presentation). For each of these a community control will be found matched on age (within bands: ≥ 2 to < 6 months, ≥ 6 to < 12 months, ≥ 1 to < 3 years, ≥ 3 to < 5 years, in 5 year bands up to age 24, and in 10 year bands at older ages), sex and place of residence. At sites where the study team's capacity enables them to recruit a larger number of controls, controls will be matched to a larger proportion of enrolled outpatients. For example, if capacity allows, one control will be found for every outpatient; or controls will be found for more than half of the outpatients, e.g. for a random sample of three-quarters of enrolled outpatients (or by selecting every second, third, and fourth outpatient, in chronological order of presentation). This approach will allow us to enhance the precision of estimates for specific primary objective 1 and specific secondary objective 1 (see also section 11.1 below on quantitative outcome measures and analysis).

Community controls will be recruited and enrolled if they, or their parents/guardians, provide informed consent.

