7.5.3 Sample collection for community controls

Diagnostic testing will be identical for controls and cases, with three exceptions: blood cultures will not be taken from controls, as the diagnostic yield is likely to be close to zero in this group; convalescent sera will not be collected from controls, as loss-to-follow-up is likely to be so high as to render results unusable; and urine will not be collected from controls.

Venous blood will be drawn from control participants as follows: Weight-based guidelines (section 7.3.2) will be used for controls ≤ 7 kg. For patients with body weight >7 kg and aged <15 years, the maximum amount of blood drawn will be 5 mL. At study sites where ethical and regulatory authorities permit, for controls with body weight >7 kg and aged ≥ 5 years and <15 years, the maximum amount of blood drawn will be 10 mL; otherwise the maximum volume for this population will also be 5 mL. For participants aged ≥ 15 years, the maximum amount of blood drawn will be 10 mL. In a randomly selected subset of 20 controls aged ≥ 15 years at each site, an additional 2.5 mL whole blood will be drawn for storage in PAXgene tubes (containing RNA stabilization solution) for eventual RNA assays; this means that for this subset of control participants, the total volume drawn will be 12.5 mL. (The number of samples collected in PAXgene tubes is limited for budgetary reasons.)

If the malaria RDT is positive for a control participant, antimalarial treatment will be offered according to national guidelines.

7.5.4 Other data collection for community controls, and estimation of population fever incidence and aetiologies

When a control participant provides blood and pharyngeal samples, study staff will collect basic demographic data (age, sex, place of residence, ethnicity). They will be asked if they have a fever and, if they answer yes, their tympanic temperature will be recorded.

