11.1 Quantitative outcome measures and analysis

Listed by study objective:

- 1) To determine the treatable and/or preventable causes of fever in children and adults presenting as outpatients, and among those admitted to hospitals, in areas represented by the study sites;

For outpatients the attributable fraction (AF) will be calculated for each pathogen or group of pathogens. This will be done separately for each site and age stratum. For each group of patients, the odds ratio (OR) for the association between each pathogen and fever will be calculated by comparing cases and controls. Logistic regression will be used to calculate the odds ratio. In order to take the matched design into account, strata based on geographical location and season will be defined at each site and the analysis will be adjusted for age, sex and stratum. Since cases and controls are recruited at a constant rate throughout the year but fever incidence is likely to vary by season, the analysis will be weighted by the proportion of patients included in the study of the total number of cases seen at the study

site in the given season. AF will then be calculated as $AF_A = p_A(1-OR_A)$. Confidence intervals will be calculated in an appropriate way, e.g. bootstrapping or delta method.

For inpatients, first the distribution of diagnoses in each site will be tabulated for all inpatients in the study. Then a second analysis to calculate AFs will be carried out for inpatients, but this will be restricted to inpatients who come from the same geographical area as the controls. The calculation of AFs for inpatients may be dropped if insufficient numbers of in-patients come from the same area as the controls.

- 2) To determine how fever aetiology varies according to patient age, level of the health system, geographical area, local malaria and HIV prevalence, and other risk factors;

Stratified analyses will be carried out as above to estimate the AF for sub-groups of patients.

- 3) To determine the prevalence and spectrum of antimicrobial resistance among bacterial pathogens identified in clinical specimens from febrile patients;

At each site the proportion of bacterial pathogens with antimicrobial resistance defined by standardized criteria will be calculated. The proportion of common organisms demonstrating resistance to a standard panel of antibiotics will be reported.

Specific secondary objectives:

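### Symptom exclusions differ between the age and care groups compared under objective 2, and controls are not screened for fever or the case exclusions, so respiratory contrasts partly reflect entry rules

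*Protocol*

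**What the plan says.** **Case entry (section 6).** Three sets of symptom rules apply.

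- Outpatients aged 15 and over need "absence of symptoms of lower respiratory infection and of diarrhoeal diseases as defined by" two items: cough with green or yellow sputum or haemoptysis, and three or more loose stools in 24 hours.
- Outpatients under 15 need only "absence of symptoms of diarrhoeal diseases as defined by" the same loose-stool count.
- Both criteria are limited to outpatients, so inpatients have no symptom exclusion. The rule "Not having been hospitalized or having undergone surgery in the previous month" applies to every patient.

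**Controls (sections 7.5 to 7.5.4).** Controls are catchment residents matched on age band, sex, place of residence and month. Beyond that, "Community controls will be recruited and enrolled if they, or their parents/guardians, provide informed consent". At the visit, "They will be asked if they have a fever and, if they answer yes, their tympanic temperature will be recorded". No rule says what happens to a febrile control, and none of the patients' symptom or recent-admission criteria is applied to controls.

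**Analysis (section 11.1).** Outpatient ORs and AFs come from case-control logistic regression, and "This will be done separately for each site and age stratum". Objective 2 is restated as "To determine how fever aetiology varies according to patient age, level of the health system, geographical area" and other factors. Its method is one sentence: "Stratified analyses will be carried out as above to estimate the AF for sub-groups of patients".

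**The concern.** A contrast between strata can be read as a difference in aetiology only if the strata admit the same kind of patient. Adult outpatients with productive cough or haemoptysis are turned away, while children with the same symptoms are enrolled. A respiratory pathogen will then look less important in adults even if the causes of fever are identical at all ages.

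The outpatient-inpatient contrast has the same problem. It affects respiratory pathogens in adults and diarrhoea-linked pathogens at both ages.

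The protocol knows the hazard. Section 3.1.2 faults earlier studies for differing inclusion criteria, and section 3.2 promises harmonised ones. They are harmonised across sites, but not across the groups compared under a primary objective. Respiratory viruses are explicit targets (sections 7.6.5 and 7.6.9) and part of the basis for the power statement in section 11.2.

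The control side is a separate and smaller matter. Cases are defined by a measured temperature of at least 37.5°C. Controls are measured only if they report fever, so some may have the condition under study without anyone knowing.

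**Working it through.** **Inputs from the protocol (section 11.2):** 600 outpatients and 300 controls per age group; prevalence 12% in cases and 5% in controls; power above 90%.

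**Assumed:** two-sided alpha 0.05; the share of patients with the excluded symptom (s); the ratio of pathogen prevalence with and without that symptom (r); the share of controls who are febrile (f). The documents give none of these. I use AF = p(1 − 1/OR), because the printed p(1 − OR) is negative whenever OR exceeds 1; that is a separate point.

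**1. The plan's own figure.** Pooled prevalence = (72 + 15)/900 = 0.0967. SE under the null = √(0.0967 × 0.9033 × (1/600 + 1/300)) = 0.0209. SE under the alternative = √(0.12 × 0.88/600 + 0.05 × 0.95/300) = 0.0183. z = (0.07 − 1.96 × 0.0209)/0.0183 = 1.59, so power is 94.4%. The stated figure reproduces. OR = (0.12/0.88)/(0.05/0.95) = 2.59, and AF = 0.12 × (1 − 1/2.59) = 7.4%.

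**2. Effect of the respiratory exclusion on a between-group contrast.** Take identical aetiology in both groups, with all-comer prevalence 12%. The restricted group shows 0.12/(1 − s + s·r), so the spurious ratio is 1 + s(r − 1). Controls stay at 5%.

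| s | r | Prevalence in restricted group | Spurious ratio | OR | AF |
|---|---|---|---|---|---|
| any | 1 | 12.0% | 1.0 | 2.59 | 7.4% |
| 10% | 2 | 10.9% | 1.1 | 2.33 | 6.2% |
| 20% | 2 | 10.0% | 1.2 | 2.11 | 5.3% |
| 20% | 3 | 8.6% | 1.4 | 1.78 | 3.8% |
| 30% | 3 | 7.5% | 1.6 | 1.54 | 2.6% |

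Since objective 2 compares AFs, the report would show 7.4% in the unrestricted group against 6.2% to 2.6% in the restricted one, with no true difference in aetiology.

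**3. Effect of febrile controls on the OR within a stratum.** Let febrile controls carry the case prevalence. Control prevalence becomes q = (1 − f) × 0.05 + f × 0.12.

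| f | q | OR | AF | Power | Power, afebrile controls only |
|---|---|---|---|---|---|
| 0 | 5.00% | 2.59 | 7.4% | 94.4% | 94.4% |
| 1% | 5.07% | 2.55 | 7.3% | 93.9% | 94.2% |
| 2% | 5.14% | 2.52 | 7.2% | 93.3% | 94.1% |
| 5% | 5.35% | 2.41 | 7.0% | 91.4% | 93.6% |
| 10% | 5.70% | 2.26 | 6.7% | 87.4% | 92.7% |

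Leaving out febrile controls restores OR 2.59 at little cost in power. Controls who have an excluded symptom act in the same direction for pathogens linked to it. The documents give no basis for sizing that part, and I have not sized it.

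**The case against.** **Are the ORs biased by the unequal entry rules?** A reader might infer so, but section 11.1 estimates them within site and age stratum. An adult-only exclusion cannot touch the child OR. In adults it changes the population that the OR and AF describe. What remains within a stratum is the lack of screening in controls.

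**Is there an age artefact for enteric pathogens?** No. Adult and child outpatients share the same loose-stool exclusion. Only the outpatient-inpatient contrast is affected, and no stool testing is described. Most named targets, such as rickettsiae, leptospires and arboviruses, are not defined by either excluded syndrome.

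**Do controls enter on consent alone?** No. They are matched catchment residents, and an unselected sample is defensible for estimating background prevalence.

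**Is the febrile-control effect worth the trouble?** It is small. At 5% febrile the AF moves by about 0.3 points, roughly a tenth of its 95% half-width of 3.6 points (delta method, 600 and 300). Self-reported fever can also be handled at analysis. That stands, except that a control who is febrile but does not say so is never measured.

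**Could a statistical analysis plan settle this?** It could define a common-criteria subset and choose which controls enter. It cannot recover a temperature or symptom that was not collected, and control data collection is fixed in this protocol.

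**Is the level-of-care contrast already limited?** Partly. Level of the health system appears in section 11.1 but not in objective 2 in sections 2 and 4.2, and inpatient AFs may be dropped. Age is in all three places.

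**Conclusion.** The point holds for between-group contrasts and, more weakly, for the control group. Followed as written, objective 2 mixes selection with aetiology for respiratory pathogens by age, and for pathogens linked to either excluded syndrome by level of care. Under the assumed ranges (10-30% excluded, pathogen 2-3 times as common in them) the artefact is a 1.1- to 1.6-fold prevalence difference. It vanishes if pathogen and symptom are unrelated. A larger figure can be produced: 30% excluded with a four-fold ratio gives 1 + 0.3 × 3 = 1.9. That is one chosen scenario, and the excluded symptom set (coloured sputum or haemoptysis) is narrower than lower respiratory illness in general.

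The documents do not support a claim that the ORs in general are biased by unequal eligibility. Failure to screen controls pulls them modestly towards 1: OR 2.59 to 2.55-2.41 and AF 7.4% to 7.3-7.0% if 1-5% of controls are febrile and carry the 12% case prevalence.

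**What to change.** **(a) Section 11.1, objective 2.** For age contrasts among outpatients in respiratory pathogens, make the comparison in patients who meet the adult-outpatient symptom criteria, and show the full groups beside it. For outpatient-inpatient contrasts, show the common-criteria subset beside the full groups, and label the full-group contrast as not comparable for respiratory and enteric pathogens. The restricted set should not replace the full inpatient group, because section 3.2 includes inpatients in order to learn the causes of severe illness and death. Section 7.3.1 records symptoms at enrolment; confirm that the form captures sputum colour, haemoptysis and stool count in children and inpatients too.

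**(b) Section 7.5.4.** Measure temperature in every control and ask the same symptom and recent-admission questions. Estimate the OR in controls who are afebrile and meet the same exclusions as the cases they are compared with, and use all controls as a sensitivity analysis. Keep all controls for background prevalence.

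**Cost.** Slightly smaller comparison sets, one analysis flag, and a few minutes per control visit. Part (b) has to be in place while controls are being enrolled, because the missing measurements cannot be obtained afterwards.
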